PROTOCOL COVER PAGE

Official Grant Title: Improving HIV treatment outcomes for people who use drugs: adapting and piloting a drug-use stigma-reduction intervention in HIV care and treatment clinics in Tanzania

NCT Number: NCT04863898

Protocol ID: 11786

Document Date: September 19th, 2023

Principal Investigator: [name], RTI International, Washington, DC

Site Principal Investigator: [name], MSc, PhD, Department of Community Health, School of Public Health and Social Sciences, Muhimbili University of Health and Allied Sciences, Implementation Science Tanzania

Co-Investigators

[name], Department of Psychiatry and Mental Health
Muhimbili National Hospital, Muhimbili University of Health and Allied Sciences

[name], RTI International, San Francisco, CA

[name], RTI International, Research Triangle Park, NC

Content

1. INTRODUCTION.....	4
1.1 Background.....	4
1.2 Study Description:.....	4
2. METHODS	7
2.1 Study design.....	7
2.2 Study population for the pilot study (Inclusion and Exclusion criteria).....	7
2.3 Study area and clinic selection	7
2.4 Sample size for the pilot study.....	7
2.6 Measures	8
2.7 Data collection.....	10
2.8 Data analysis (see Statistical Analysis Plan)	10
2.9 Ethical considerations	10
2.10. Study limitations and mitigation.....	11
3. DISSEMINATION PLAN	11

Abstract

Background

Globally, people who used drugs (PWUD) face high levels of drug use stigma. Drug use stigma, including experienced, anticipated, perceived, and internalized, has been documented as a barrier to linkage and retention in Medication Assisted Treatment (MAT), needle and syringe exchange programs, HIV care and treatment services, and general health care and is negatively associated with physical and mental health outcomes among PWUD.

Reducing drug use stigma in HIV care and treatment clinics (CTCs) will improve access to and retention in HIV treatment services for PWUD, a key population at elevated risk for HIV, thereby improving individual health outcomes, reducing onward transmission of HIV, and contributing to achievement of the global and national 95-95-95 targets. We propose to address the drug use stigma barrier in HIV CTCs by adapting and testing an HIV stigma-reduction intervention to focus on drug use stigma-reduction.

Objectives (AIMS)

1. To adapt a health facility HIV stigma-reduction participatory training intervention to address drug use stigma in HIV CTCs.
2. To evaluate the acceptability, appropriateness, and feasibility of the adapted drug use stigma-reduction intervention.

Methods

Study design and procedures: Guided by the ADAPT-ITT model, which provides a framework and prescriptive method for adapting evidence-based interventions (EBIs), we will employ a mixed methods design to adapt, and pilot test the intervention, including pre-post surveys with CTC staff and post intervention focus group discussions. A formative (qualitative) phase of research will be conducted with PWUD and clinical and non-clinical CTC staff to inform the first step in the adaption of the HIV stigma-reduction intervention to focus on drug-use stigma. We will pilot the adapted participatory training intervention for health care staff in seven high-volume HIV clinics in areas with the highest concentration of PWUD in Dar-es-Salaam, the Ilala, Kinondoni, and Temeke Municipal Councils.

Measurements: The key outcome measures will be three scales to measure stigma and a self-assessed and reported measure of knowledge of drug use. In addition, we propose to collect socio-demographic characteristics, a measure of social desirability bias, and level of contact with PWUD. The implementation outcome measures will be feasibility, acceptability, and appropriateness of the intervention.

Data analysis: Qualitative data will be analyzed using a multi-stage, modified grounded theory approach. To confirm the validity of the scales we will conduct confirmatory factor analyses (CFA) on the scales we do not modify and exploratory factor analyses (EFA) on those that we do. To examine the intervention effect, we will fit linear mixed effect regression models using the R package lme4 to examine changes in outcome measures from pre- to post-intervention while controlling for repeated measurements via random intercepts by individual. Each model will control for type of clinic, type of staff (clinical vs. non-clinical), gender, age, years of service in health facilities, years of service in an HIV

clinic, social desirability, level of contact with PWUD, and number of clients who use drugs treated within the last month. In addition, to identify possible effect modifiers (e.g., staff type, gender, level of contact with drug users), we will test time by modifier interaction terms within these models.

1. Introduction

1.1 Background

The goal of this study is to adapt and pilot an effective health facility HIV stigma-reduction intervention to address drug use stigma in HIV Care and Treatment clinics (CTCs) in Tanzania, a barrier to linkage and retention in HIV care for People Living with HIV (PLWH) who use drugs. In Tanzania, there are an estimated 300,000 People who use Drugs (PWUD), primarily heroin. Although most heroin is inhaled or ingested, an estimated 10% (30,000) of PWUD inject. HIV prevalence among PWUD who do not inject (18-25%) and those who do inject (35%) is 4-7 times higher than in the general population (5%). PWUD face high levels of stigma, including when they try to seek HIV treatment at HIV CTCs, presenting a barrier to linkage and retention in HIV treatment for this highly HIV vulnerable group. Therefore, reducing drug use stigma in HIV CTCs is critical to improving access to and retention in HIV treatment services for PWUD. In response to this need, the investigators will:

AIM 1: Adapt a health facility HIV stigma-reduction participatory training intervention to address drug use stigma in HIV CTCs

AIM 2: Pilot test the adapted drug use stigma-reduction intervention for acceptability, appropriateness, and feasibility

The investigators will achieve Aim 1 through a systematic, multi-stage adaptation process that will include a formative phase of in-depth interviews with PLWH who use drugs and CTC staff to inform initial adaptation of the Health Policy Plus (HP+) intervention.

Stakeholders, including PLWH who use drugs and CTC staff, will provide feedback on the initial materials through a participatory workshop, leading to a training manual that will be reviewed by topic experts and then finalized. Experienced Tanzanian HIV stigma-reduction trainers will deliver the intervention to CTC staff. The pilot test will include health workers based in seven CTCs in Dar-es-Salaam. A mixed methods evaluation will comprise pre-post surveys, observation of trainings, and post-training focus group discussions with intervention participants and trainers. Changes in CTC staff's mean scores on stigma scales from pre- to post-intervention will be assessed, along with measures of intervention acceptability, appropriateness, and feasibility. Focus groups will explore themes around the experience of participating in the drug use stigma-reduction training.

1.2 Study Description:

The goal of this R21 application is to adapt and pilot an effective health facility HIV stigma reduction intervention to address drug use stigma in HIV CTCs in Tanzania, a barrier to linkage and retention in HIV care PLWH who use drugs. Reducing drug use stigma in HIV CTCs will improve access to and retention in HIV treatment services for PWUD, a key

population at elevated risk for HIV, thereby improving individual health outcomes, reducing onward transmission of HIV, and contributing to achievement of the global and national 95-95-95 targets. The investigators propose to do this by adapting (Aim 1) and testing for acceptability, appropriateness and feasibility (Aim 2) a drug use stigma-reduction intervention for HIV CTCs, guided by the eight-step ADAPT-ITT model. The study has two phases. First, the investigators will adapt the participatory training from an evidence-based health facility HIV stigma-reduction intervention (the HP+ total facility approach) to address drug use stigma among HIV CTC staff and then pilot test it in seven CTCs in three municipalities of Dar-es-Salaam. The first seven steps of the ADAPT-ITT model will guide AIM 1—the adaptation process, and step eight will guide AIM 2.

Step 1: Assess. Formative research will provide contextual information from PLWH who use drugs and CTC staff, to inform the adaptation of the HP+ intervention to focus on drug use stigma. Given the sensitivity of the topic and concerns about privacy and confidentiality, the investigators will employ individual in-depth interviews with both PLWH who use drugs and CTC staff.

In-depth interviews with PLWH who use opioids: 18 respondents aged 18 or older in the following categories: Medicated Assisted Therapy (MAT) clients living with HIV who get HIV treatment at CTCs; MAT clients not on HIV treatment; PLWH who use opioids who are not on MAT or HIV treatment. With PLWH the investigators will seek to understand the types of drug use stigma (experienced, anticipated, and perceived) that they encounter in relationship to CTCs, the specific manifestations of those types of stigma, and how this stigma influences HIV care linkage and retention among respondents living with HIV. The investigators will also explore what respondents view as driving drug use stigma in CTCs.

In-depth interviews with CTC staff: Fourteen staff from the high-volume clinics located in areas where people who use drugs congregate or live, who have direct interactions with clients split by type of staff (clinical and non-clinical). The in-depth interviews will focus on capturing stigmatizing attitudes and practices toward PWUD and understanding the underlying drivers of drug use stigma in CTCs (e.g., fear, lack of knowledge, attitudes and beliefs), as well as the who, when, and where drug use stigma occurs in the course of staff-client interactions.

All interviews will be recorded, transcribed, and translated. A multi-stage modified grounded theory approach to analysis will be deployed. An initial rapid qualitative analysis will be conducted followed by inductive and deductive development of initial codebooks. Coding and analysis will continue iteratively to discover additional themes and issues. The findings will be described in thematic summaries, tables, and diagrams.

Step 2: Decision. Guided by the formative results and the study team's experience working with service delivery for PWUD and developing and adapting stigma-reduction intervention tools for a range of audiences, the study team will conduct the first round of adaptation of the HP+ intervention training curriculum materials. The investigators will develop five, 2.5-hour participatory training modules that can be delivered flexibly across multiple partial days of training. Existing HP+ participatory training modules will be assessed for their appropriateness in terms of training modality (e.g., discussion, role play, reflection) and the specific content that needs to be adjusted (e.g., case studies, pictures, drivers of stigma) to

focus on drug use stigma. New materials for identified gaps will be developed, for example, around drug use as a medical condition.

Step 3: Administer. Next, the training materials will be put through a dry run—a 2-day participatory stakeholder workshop with key stakeholders, including HIV CTC staff, people with lived experience of drug use, Community Based Organization staff providing services to PWUD, MAT medical providers, and municipality and ministry of health representatives. Workshop participants will be asked to provide feedback on their overall perceptions and experience of the training (e.g., did it resonate, was it engaging, did it cover the right topics, exercises that should be dropped, gaps that remain to be filled). They will also be asked to comment on the approach and content of each specific exercise, including relevance, appropriateness, and content (including any visual materials).

Step 4: Produce. The study team will review and discuss stakeholder workshop feedback, refining the training manual in response.

Step 5: Topical experts. Two HIV stigma-reduction training experts will review the adapted manual to provide feedback on its congruence with stigma-reduction training principles, the scientific literature, and observed experience of PWUD trying to access HIV treatment.

Step 6: Integrate will involve a final revision of the manual incorporating feedback from the topical experts.

Step 7: Trainers, Kimara Peer's two stigma-reduction master trainers and a MAT provider expert and the Principal Investigator (PI) and site PI will work together to finalize training plans.

Step 8: Pilot test. The drug-use stigma-reduction intervention will be delivered in seven HIV CTCs with high client loads located in areas within the three identified municipalities where PWUD congregate or live. These types of CTCs have on average 20 to 25 staff (clinical and non-clinical) who come into direct contact with clients. Staff of all levels will be trained together, which has been shown to have multiple benefits. Training will be on site at the facility and delivered to all relevant staff together in five, 2.5-hour participatory sessions. Timing of the sessions will be negotiated with each facility to ensure minimal disruption to service delivery, as has been done successfully for the HP+ intervention. Training will be delivered by two master trainers from a local community-based organization (Kimara Peers) who have 20 years of delivering HIV stigma-reduction training, including to health workers, and who also run outreach services and a drop-in center for PWUD and a MAT provider, and an addiction specialist. The training team will include people of lived experience of drug use, who will participate as a panel in one of the sessions.

A mixed-methods approach will be used for assessment: pre-post intervention surveys, training observation, and focus group discussions with intervention participants and trainers. Trainers will complete a process rating form at the end of each session focusing on issues of feasibility, coverage of session content, disruptions, issues raised during the session, and level of participant engagement with the material. The training team will maintain attendance rosters for each session, noting when participants leave the room and whether and when they return. The site PI and a member of the field staff will each observe, between them, half of all sessions across the seven facilities, recording observations on the same issues

captured by the facilitators, as well as facilitator fidelity to the training manual material and facilitator-participant interaction. Participant views on the training will be captured through focus groups, one in each facility (8-12 intervention participants per group of clinical and non-clinical staff). Focus groups will be recorded, transcribed, translated, and analyzed using the same process described above for formative work in Aim 1. Topics will focus on acceptance and appropriateness of training modalities and content, as well as areas where participants wanted more focus. Questions on the length and timing of sessions will also be discussed.

2. Methods

2.1 Study design

This is a mixed methods pre-post study design (single arm) with HIV care and treatment clinic (CTC) staff, both clinical and non-clinical. Data collection will include a pre(baseline) survey and a post-intervention (endline) survey conducted three months after completion of an intervention in a clinic and focus group discussions with CTC staff who participated in the training post intervention. A mixed methods approach is used because of the nature of the proposed study which combines adapting an HIV stigma-reduction intervention to address drug-use stigma and conducting a preliminary pilot study to test the intervention adaptation. Hence, we will employ surveys to collect pre and post intervention data and then conduct focus groups to help us deepen our understanding of how staff who participated in the intervention experienced it.

2.2 Study population for the pilot study (Inclusion and Exclusion criteria)

The pilot training intervention will be delivered to CTC staff.

The inclusion criteria for CTC staff will be having duties of provision of health services that include having direct contact with clients seeking HIV treatment services, whether they are dedicated CTC staff or shared staff within the wider facility (e.g., lab, guards) and being 18 years or older. The exclusion criteria will be being mentally incompetent or refusal to consent.

2.3 Study area and clinic selection

The study will be conducted in Dar-es-Salaam, in the Ilala, Kinondoni, and Temeke Municipal Councils. These are the areas the highest concentration of PWUD. The study area has 140 CTCs and three MAT clinics. CTCs and MAT clinics are governed by the municipalities. The intervention will be piloted in seven high-volume HIV clinics in areas with the highest concentration of PWUD. The seven clinics will be selected through a two-step process. Based on existing data on location of where higher concentrations of PWUD live, we will map each CTC's distance from a high drug use area. We will then take the list of all CTCs that would provide close and easy access to the largest concentrations of PWUD (within 5Km) and randomly select the 7 study facilities.

2.4 Sample size for the pilot study

Sample size for the pre- and post-surveys of the intervention was calculated using the PASS software program,(98) we estimated the power for comparisons of mean scale scores from pre- to post-intervention, assuming a p-value of 0.05 and a final sample size of 131 with both measurements (i.e., 13% attrition from the initial sample size of 150). We would have 85% power to detect a small-to-medium sized effect based on standardized mean difference ($d=0.32$). (99)

We are therefore targeting baseline enrollment of a150 health workers working in seven CTCs in Dar-es-Salaam. Health workers will be randomly selected on the day of baseline data collection at each facility. A mixed methods evaluation will comprise pre-post surveys (n=150 at each round), observation of trainings, and post-training focus group discussions with intervention participants (n=7; 8–12 participants each) and trainers (n=1; 6 participants).

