STATISTICAL ANALYSIS PLAN

Official Grant Title: Improving HIV treatment outcomes for people who use drugs: adapting and piloting a drug-use stigma-reduction intervention in HIV care and treatment clinics in Tanzania

NCT Number: NCT04863898

Protocol ID: 11786

Document Date: September 19th, 2023

Principal Investigator: [name], RTI International, Washington, DC

Site Principal Investigator: [name], MSc, PhD, Department of Community Health, School of Public Health and Social Sciences, Muhimbili University of Health and Allied Sciences, Implementation Science Tanzania

Co-Investigators

[name], Department of Psychiatry and Mental Health
Muhimbili National Hospital, Muhimbili University of Health and Allied Sciences

[name], RTI International, San Francisco, CA

[name], RTI International, Research Triangle Park, NC

Statistical Design and Power

The first phase of the study will be qualitative, so will not involve any statistical analysis. The second phase of the study uses mixed methods to evaluate the pilot intervention, so power analysis was calculated only for the survey portion of the evaluation.

Power Analysis

Using the PASS software program, we estimated the power for comparisons of mean scale scores from pre- to post-intervention, assuming a p-value of 0.05 and a final sample size of 131 with both measurements (i.e., 13% attrition from the initial sample size of 150). We would have 85% power to detect a small- to medium-sized effect based on standardized mean difference ($d=0.32$).

Statistical Analysis

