We will collect outcome measures through baseline and endline surveys (collected 3 months after the intervention is complete in each facility) with HIV care and treatment (CTC) staff using three validated scales (the Opening Minds Scale for health providers (OMS-HC), a modified Bogardus Social Distance Scale, and the Addiction Belief Scale). We hypothesize that respondents' scores on these scales will decrease between the pre- and post-intervention surveys, which would represent a reduction in drug use stigma. In addition, we will include a survey section on self-assessed and self-reported degree of knowledge about drug use and how to provide services to people who use drugs, which we hypothesize would increase between the pre- and post-intervention surveys. Given the sensitive nature of questions about drug use, we include a version of the Marlowe-Crowne Social Desirability scale validated in the East African context for use as a control. As contact with people of a stigmatized group often decreases stigma felt toward that group, we include a measure of contact with people who use drugs. We will also collect socio-demographic measures on participants' sex, age, education, religion, position in the HIV care and treatment clinic (CTC) (clinical vs non-clinical staff), length of service in health care, length of service in HIV CTC, and frequency of contact in the CTC with clients who use drugs. At endline only, measures of intervention acceptability, appropriateness, and feasibility will be asked. Endline data will be collected 3 months after the intervention is complete in each facility.

As the scales have not been previously validated in the Tanzanian context, we will modify them based on the formative research and consultation with experts in Tanzania. The validity of the scales will be confirmed through confirmatory factor analyses (CFA) on the scales we do not modify and exploratory factor analyses (EFA) on those we do. Exploratory factor analyses will be conducted in SAS version 9.4, applying a Promax rotation with the final number of factors selected based on variance explained, scree plot, and interpretability of the factors. Confirmatory factor analyses will be conducted using Mplus version 8.6. Model fit will be assessed based on the comparative fit index (CFI), Tucker-Lewis fit index (TLI), and root mean square error of approximation (RMSEA).

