We will calculate descriptive statistics for all collected variables: counts and percentages for categorical variables, means and standard deviations for continuous variables. We will also calculate participants' scale responses using additive or averaging methods as recommended by the literature. To examine the changes in our outcome variables between the pre-intervention and post-intervention surveys, we will fit linear mixed effect regression models using the R package *lme4* with each outcome variable as our dependent variable and time (pre- vs. post-intervention) as our primary independent variable. In these linear mixed effect regression analyses, we will control for repeated measures by individuals by including random intercepts by individual respondent; all other parameters will be included as fixed effects. We will use the function *lme4::confint* to generate bootstrapped 95% confidence intervals with 1,000 replicates. To assess model fit, we will use likelihood ratio tests (alpha = 0.05). We will visually inspect residual plots for homoscedasticity and normality.

In addition to univariate regression analyses for each of our outcomes of interest, we will conduct regression analyses that control for clinic, type of staff, gender, age, years of service in health facilities, years of service at an HIV health clinic, number of clients who use drugs treated within the last month, and social desirability bias. In addition, we will individually test each control parameter for an interaction with time, which would indicate a differential change in the outcome of interest over time by the parameter in question.

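### Is the stated 85% power at odds with its own inputs of 131 pairs, alpha 0.05 and d = 0.32?

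*Protocol*

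**What the plan says.** Protocol 2.4 says the calculation was done in PASS for pre-to-post comparisons of mean scale scores, "assuming a p-value of 0.05 and a final sample size of 131 with both measurements". The 131 comes from 150 enrolled less 13% attrition. The result reads "We would have 85% power to detect a small-to-medium sized effect based on standardized mean difference", with d = 0.32. The SAP (Power Analysis) repeats the same figures: "We would have 85% power to detect a small- to medium-sized effect based on standardized mean difference".

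Neither document names the test, its sidedness, the SD behind d, the assumed pre-post correlation, or any allowance for clinics or for several outcomes. The SAP (Statistical Analysis) states a directional hypothesis, "We hypothesize that respondents' scores on these scales will decrease between the pre- and post-intervention surveys". It plans a linear mixed model in which "we will control for repeated measures by individuals by including random intercepts by individual respondent", and uses the bootstrap "to generate bootstrapped 95% confidence intervals with 1,000 replicates". Protocol 2.4 also describes "pre-post surveys (n=150 at each round".

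**The concern.** A reader who checks the sentence in the usual way gets a different answer. The study has one arm and each person is measured twice, so the natural check is a paired t-test, with d read as mean change over the SD of change. That gives 95.3% two-sided or 97.7% one-sided. The gap from 85% is far too large to be rounding or a normal approximation.

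This is the only power figure in either document, and the baseline target of 150 is presented as following from it. If it were wrong, the stated detectable effect would be wrong too, and a null result on the stigma scale, which is a primary outcome, would be harder to read. The 150 per round seems to add a second inconsistency, because the same section expects only 131 people to have both surveys.

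**Working it through.** **Inputs.** From Protocol 2.4 and the SAP: 150 enrolled, 131 complete pairs, alpha 0.05, d = 0.32, power 85%. The sidedness, SD basis and pre-post correlation ρ are not given, so they are varied below as assumptions.

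**Attrition.** 150 × 0.87 = 130.5, and 1 − 131/150 = 12.7%. This agrees with the stated 13%.

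**Reading A: d on the SD of change.** The paired t-test has 130 df and noncentrality d√n = 0.32 × √131 = 0.32 × 11.45 = 3.66.

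- Power is 95.3% two-sided and 97.7% one-sided. The normal approximation gives 95.6% and 97.8%, so the method of calculation is not the cause.
- Turned round, 85% power with 131 pairs corresponds to d = 0.264 two-sided or 0.235 one-sided.
- At d = 0.32, 90 pairs would be enough for 85% two-sided.

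The stated figure is not reproduced on this reading.

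**Reading B: d on the SD of the scale score.** With equal variances at the two surveys, the SD of change is SD × √(2(1 − ρ)). The effect entering the paired test is therefore 0.32 / √(2(1 − ρ)).

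| Assumed ρ | Two-sided power | One-sided power |
|---|---|---|
| 0 | 72.9% | 82.4% |
| 0.1 | 77.3% | 85.8% |
| 0.2 | 82.0% | 89.2% |
| 0.3 | 86.7% | 92.4% |
| 0.5 | 95.3% | 97.7% |

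Two-sided power is 85% at ρ = 0.264: √(2 × 0.736) = 1.213, and 0.32 / 1.213 = 0.264, the detectable value found under Reading A. Any ρ from 0.22 to 0.31 gives 83% to 87%. One-sided, 85% needs ρ of about 0.08.

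**Other routes to about 85%, with d on the SD of change, two-sided.**

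- A smaller alpha: 0.01 gives 85.1% and 0.0125 gives 86.9%. The SAP lists three scales and a knowledge measure, so an allowance for several outcomes is conceivable. However, the printed alpha is 0.05.
- A clinic allowance: the design effect would be (0.32 / 0.2638)² = 1.47. With 131/7 = 18.7 people per clinic, that is an intraclass correlation of 0.47 / 17.7 = 0.027.

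**A route that fails.** Treating the surveys as independent samples of 131 gives 73.2% two-sided and 82.6% one-sided. It also ignores the pairing that the text states.

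**Does anything depend on the answer?** Protocol 1.2 (Step 8) puts client-facing staff at 20 to 25 per clinic on average, so seven clinics hold about 7 × 20 = 140 to 7 × 25 = 175. A target of 150 is already most of the available staff. The SAP's analysis uses neither the assumed d nor ρ.

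**The 150 per round.** One number counts people surveyed at a round and the other counts people with both surveys. They can differ without contradiction, for example if some endline respondents have no baseline survey. The documents do not say whether that is intended.

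**The case for a change.** The strongest case for a change is that every route to 85% needs something the documents do not print, or replaces something they do. Power calculations are published so that others can check them, and this one cannot be checked. The effect of the omission is not trivial either. At 85% power two-sided, the detectable difference on the score SD is 0.264 × √(2(1 − ρ)): 0.37, 0.33, 0.26 or 0.20 for ρ of 0, 0.2, 0.5 or 0.7. That is almost a twofold range, and at ρ = 0 the power for d = 0.32 is only 73%.

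The arithmetic stands, and so does the point that the sentence is incomplete. The step from incomplete to wrong does not. The text speaks of comparing mean scale scores and never mentions change scores, so the score SD is at least as natural a reading, and a modest positive correlation between two surveys of the same people then gives the printed figure. Replacing 85% with 95%, or 0.32 with 0.264, would assume that no further input was entered in PASS, and it could turn a correct number into an incorrect one. Changing 150 per round to 131 could likewise lower an intended survey target. A null result will be judged from the planned 95% confidence intervals, which reflect the variability and correlation actually observed.

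**Conclusion.** The concern does not call for a change. The printed inputs leave power undetermined: 95.3% two-sided if d is on the SD of change, and 73% to 95% if it is on the score SD with ρ between 0 and 0.5. The stated 85% lies inside that range and is met at ρ = 0.264. If the SD-of-change reading is right, the plan understates its power by about 10 points, which is the harmless direction. Power falls below 85% only if d is on the score SD with ρ under about 0.26 two-sided (0.08 one-sided), or if clinic or multiplicity effects go beyond what was allowed for. The documents establish neither.

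These figures assume 131 complete pairs, a paired t-test and, under Reading B, equal variances at the two surveys. No reading alters enrolment, data collection, the mixed model or the intervals. This is also a single-arm pilot whose second aim is acceptability, appropriateness and feasibility, which the power figure does not address. The missing inputs are in the PASS run and can be reported with the results. The 150 per round is at most loose wording.

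### Does planning for 131 people measured twice conflict with a survey of 150 at each round?

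*Protocol*

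**What the plan says.** Protocol 2.4 and the Power Analysis section of the SAP both assume "a final sample size of 131 with both measurements (i.e., 13% attrition from the initial sample size of 150" and state 85% power for a standardized mean difference of 0.32. Protocol 2.4 sets the intake: "We are therefore targeting baseline enrollment of a150 health workers working in seven CTCs in Dar-es-Salaam". It describes selection at one time point only: "Health workers will be randomly selected on the day of baseline data collection at each facility". It then summarises the evaluation: "A mixed methods evaluation will comprise pre-post surveys (n=150 at each round), observation of trainings". The SAP gives no endline number.

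The SAP fits linear mixed models, "including random intercepts by individual respondent; all other parameters will be included as fixed effects". Of the four primary outcomes in Protocol 2.5, three are collected after the intervention only: "At endline only, measures of intervention acceptability, appropriateness, and feasibility will be asked".

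Three further provisions bear on the point:
- Under Step 8 of Protocol 1.2, the training goes to all relevant staff of a facility together and is not limited to survey respondents.
- The same step has the trainers keep an attendance roster for every session.
- Protocol 2.5 has the endline questionnaire ask in more detail about participation in the pilot training.

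**The concern.** Read literally, one section gives two endline samples. With 150 enrolled and 13% lost, about 131 people answer at endline. A survey of 150 at that round would need 19 respondents who were never surveyed before. No procedure for choosing them is given, and no rule says how they would be analysed. A random-intercept model accepts people with a single measurement without any special step, so they would enter by default.

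Two things could be at stake. The first is who contributes to the pre-post comparison of the stigma and knowledge scales. If the added staff had not been trained, they would pull the estimated change towards zero. The second is who rates acceptability, appropriateness and feasibility, since people who did not attend cannot rate the training. The clinic sizes in Protocol 1.2 also raise the question of whether enough unsurveyed staff exist.

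**Working it through.** **Inputs.** Baseline 150, attrition 13%, 131 pairs, alpha 0.05, power 85% and d = 0.32 (Protocol 2.4; SAP, Power Analysis). Seven clinics with 20 to 25 direct-contact staff on average (Protocol 1.2, Step 8). Assumptions not in the documents: a two-sided test, and a pre-post correlation r of 0.25 or 0.5.

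**Step 1: the plan's own figures.** 150 × (1 − 0.13) = 130.5, which rounds to 131. In reverse, (150 − 131)/150 = 19/150 = 12.7%, printed as 13%. These agree. By noncentral t, 85% power with 131 pairs implies a mean change of 0.2638 SDs of the paired differences. This matches d = 0.32 in raw-score SDs if r is about 0.264: 0.32/√(2 × (1 − 0.264)) = 0.2638. The 85% is taken as given below, with 0.2638 held fixed.

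**Step 2: nobody added, complete pairs only.** 131 pairs give 85.0%, the stated figure.

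**Step 3: nobody added, SAP model.** The 19 people lost to follow-up still contribute their baseline. Write a = 131, m = 19 and p = a/(1 − r²). The variance of the change, in raw-score variance units, is v = [2p(1 − r) + m]/[p(a + m)], and the effective number of pairs is 2(1 − r)/v.
- r = 0.25: p = 139.73, v = 228.6/20960 = 0.010907, effective pairs 137.5, power 86.7%.
- r = 0.5: p = 174.67, v = 193.67/26200 = 0.007392, effective pairs 135.3, power 86.1%.

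**Step 4: 19 added who change like the rest.** With 19 baseline-only and 19 endline-only people, the effective number of pairs is a + m(1 − r).
- r = 0.25: 131 + 14.25 = 145.25, power 88.4%.
- r = 0.5: 131 + 9.5 = 140.5, power 87.4%.

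Leaving these people out therefore costs 88.4 − 86.7, about 1.8 points, or 87.4 − 86.1, about 1.3 points (differences taken before rounding).

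**Step 5: 19 added, all untrained and unchanged.** The weight of the endline-only people in the estimate is m(1 − r)/[a + m(1 − r)].
- r = 0.25: 14.25/145.25 = 9.8% dilution, power 81.3%.
- r = 0.5: 9.5/140.5 = 6.8% dilution, power 82.5%.

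**Step 6: endline-only ratings.** With the same spread, a mean from 131 rather than 150 respondents has a standard error larger by √(150/131) = 1.07, or 7%.

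**Step 7: staff pool.** 7 × 20 = 140 and 7 × 25 = 175. Enrolling 150 and adding 19 needs 169 people, or 169/7 = 24.1 per clinic.

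**The case for a change.** The strongest case for a change is that three of the four primary outcomes exist only at endline, so whoever is surveyed then is their denominator. That could be 131 people or 150, and the text does not settle it. Attendance is recorded, but no rule uses it to decide who may rate the training. If the pool of trained colleagues is exhausted, new hires are a likely source of additions, and they would be the untrained respondents of Step 5. One sentence would remove the doubt.

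Part of this stands. The wording does not say whether 150 at endline is the number approached or a replenished sample, and no endline selection is described. The consequences are weaker than they look:

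- **Dilution.** Colleagues outside the survey sample are, by plan, offered the training. The rosters and the endline participation questions identify anyone who missed it. Nothing in the documents implies that all 19 would be untrained.
- **Ratings of the training.** Asking these of people who attended is what an analyst would do with the planned attendance data. The choice between 131 and 150 changes a standard error by 7%.
- **Staff pool.** The figures are general: "These types of CTCs have on average 20 to 25 staff (clinical and non-clinical) who come into direct contact with clients". They are not counts for the seven selected clinics. Eligibility also covers people "whether they are dedicated CTC staff or shared staff within the wider facility", and it is not stated whether the average includes the shared staff. No shortfall is shown. A small pool would make a top-up less likely and so favour the 131 on which the power already rests.

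**Conclusion.** No change to the plan is needed. Protocol 2.4 is loosely worded about the endline survey, but its arithmetic is sound: 131 is 150 less 13%, and the power is tied to 131 pairs. No analysis in either document uses an endline number of 150.

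Either way of carrying out the survey gives a sound result. Without additions, power is the stated 85%, or about 86-87% once the model uses the baseline-only respondents. With 19 trained additions it is about 87-88%. A closed cohort therefore costs 1.3 to 1.8 points against a replenished one, which is a fair trade-off in a single-arm pilot. The adverse figure of 81-83%, with the change diluted by 7-10%, belongs to an extreme case that the plan does not imply and that its attendance data would reveal.

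This rests on the stated 85% taken as given, a two-sided test, a correlation of 0.25 to 0.5, and training delivered to all relevant staff as Protocol 1.2 intends. The gap is one of detail, which the analysts can fill by reporting the endline number obtained and how many respondents have both measurements.
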